#### **4.4. Efficacy Variables**

##### **4.4.1. Primary Efficacy Variable**

The primary endpoint in the study is:

- Proportion of patients with IGA 0 or 1 (on a 5-point scale) at week 16

For the ex-US countries, the co-primary endpoints are:

- Proportion of patients with EASI-75 ( $\geq 75\%$  improvement from baseline) at week 16
- Proportion of patients with IGA 0 or 1 (on a 5-point scale) at week 16

##### Investigator's Global Assessment (IGA)

The IGA is a static 5-point assessment instrument to rate AD disease severity globally in clinical studies. The ratings (0 = clear, 1 = almost clear, 2 = mild, 3 = moderate, 4 = severe) are an overall assessment of AD skin lesions based on erythema and papulation/infiltration. IGA score will be assessed at the scheduled and unscheduled clinic visits according to [Appendix 10.2](#).

##### Eczema Area and Severity Index (EASI)

The EASI is a validated measure used in clinical practice and clinical trials to assess the severity and extent of AD ([Hanifin 2001](#)). The EASI score calculation is based upon the Physician's Assessment of Individual Signs [erythema (E), induration/papulation (I), excoriation (X), and lichenification (L)], where each sign is scored as 0 = Absent, 1 = Mild, 2 = Moderate, or 3 = Severe, and also upon the Area Score [based on the % (BSA) affected] where 0 = 0% BSA, 1 = 1-9% BSA, 2 = 10-29% BSA, 3 = 30-49% BSA, 4 = 50-69% BSA, 5 = 70-89% BSA, 6 = 90-100% BSA.

For each major section of the body (head, upper extremities, trunk and lower extremities), EASI score = (E+I+X+L) x Area Score. The total EASI score is the weighted total of the section EASI using the weights 10% = head, 20% = upper extremities, 30% = trunk, 40% = lower extremities. The minimum possible EASI score is 0 and the maximum possible EASI score is 72 where a higher score indicates increased extent and severity of atopic dermatitis. The EASI score of each sign (E, I, X and L) can be calculated in a similar way, for example, the EASI score of erythema = weighted sum of E x Area Score at each section.

The EASI will be collected at the scheduled and unscheduled clinic visits according to [Appendix 10.2](#).

#### 4.4.2. Secondary Efficacy Variables

The key secondary endpoints are:

- Proportion of patients with EASI-75 ( $\geq 75\%$  improvement from baseline) at week 16 (this is not a secondary endpoint for ex-US countries as it is already a co-primary endpoint)
- Percent change in EASI score from baseline to week 16
- Percent change from baseline to week 16 in weekly average of daily peak Pruritus NRS
- Proportion of patients with improvement (reduction) of weekly average of daily peak Pruritus NRS  $\geq 3$  from baseline at week 16
- Proportion of patients with improvement (reduction) of weekly average of daily peak Pruritus NRS  $\geq 4$  from baseline at week 16

##### Peak Pruritus Numeric Rating Scale (NRS)

The Peak Pruritus NRS is a simple assessment tool that patients will use to report the intensity of their pruritus (itch) during a 24-hour recall period. Patients will be asked the following questions:

- For maximum itch intensity: “On a scale of 0 to 10, with 0 being ‘no itch’ and 10 being the ‘worst itch imaginable’, how would you rate your itch at the worst moment during the previous 24 hours?”

Patients will be instructed on using the patient diary to record their Pruritus NRS score at the baseline visit. Patients will complete the rating scale daily throughout the entire study (screening period, treatment period, and follow-up period). Clinical sites will check and remind patients to complete the diary at each visit.

For each day, if there are multiple NRS scores collected on the same day, the maximum value of all the scores collected will be used for analysis.

The baseline NRS is defined as the prorated average of the NRSs reported continuously for 7 days right before and on the baseline visit (i.e. study day -6 to day 1). For post-baseline NRS, the mean weekly NRS is calculated as the prorated average of the reported daily NRS within the week. For example, if there are 3 scores in a week, the prorated average =  $(\text{score1} + \text{score2} + \text{score3})/3$ .

Other secondary endpoints are:

- Proportion of patients with EASI-50 at week 16
- Proportion of patients with EASI-90 at week 16
- Time to onset of effect on pruritus as measured by proportion of patients with improvement (reduction) of weekly average of daily peak Pruritus NRS  $\geq 3$  from baseline during the 16-week treatment period

- Time to onset of effect on pruritus as measured by proportion of patients with improvement (reduction) of weekly average of daily peak Pruritus NRS  $\geq 4$  from baseline during the 16-week treatment period
- Change from baseline to week 16 in percent BSA affected by AD
- Percent change from baseline to week 16 in SCORAD
- Change from baseline to week 16 in CDLQI
- Change from baseline to week 16 in POEM
- Change from baseline to week 16 in weekly average of daily peak Pruritus NRS
- Percent change from baseline to week 4 in weekly average of daily peak Pruritus NRS
- Change from baseline to week 16 in HADS
- Proportion of patients with improvement (reduction) of weekly average of daily peak Pruritus NRS  $\geq 4$  from baseline to week 4
- Incidence of skin-infection TEAEs (excluding herpetic infections) through week 16\*
- Incidence of serious TEAEs through week 16

\*It will be adjudicated by study medical director.

#### BodySurfaceArea(BSA)InvolvementofAtopicDermatitis

Body surface area affected by AD will be assessed for each section of the body (the possible highest score for each region is: head and neck [9%], anterior trunk [18%], back [18%], upper limbs [18%], lower limbs [36%], and genitals [1%]) and will be reported as a percentage of all major body sections combined.

Total BSA will be the sum of all individual body areas. Patients will undergo this assessment at the scheduled and unscheduled clinic visits according to [Appendix 10.2](#).

#### SCORingAtopicDermatitis(SCORAD)

The SCORAD is a validated tool used in clinical research and clinical practice that was developed to standardize the evaluation of the extent and severity of AD ([Dermatology 1993](#)). The extent of AD is assessed by the Investigator as a percentage of each defined body area and reported as the sum of all areas, with a maximum score of 100% (assigned as “A” in the overall SCORAD calculation). The severity of 6 specific symptoms (erythema, oedema/papulation, excoriations, lichenification, oozing / crusts and dryness) of AD is assessed by the Investigator using the following scale:

- 0: None
- 1: Mild
- 2: Moderate
- 3: Severe

A maximum of 18 total points, assigned as “B” in the overall SCORAD calculation.

Subjective assessment of itch and sleeplessness is recorded for each symptom by the patient or relative on a visual analogue scale (VAS), where 0 is no itch (or sleeplessness) and 10 is the worst imaginable itch (or sleeplessness), with a maximum possible score of 20. This parameter is assigned as “C” in the overall SCORAD calculation. The SCORAD is calculated as  $A/5 + 7B/2 + C$ . The maximum SCORAD score is 103. The objective SCORAD is calculated as  $A/5 + 7B/2$ . The maximum objective SCORAD score is 83.

Patients will undergo this assessment at the scheduled and unscheduled clinic visits according to [Appendix 10.2](#).

#### Children’sDermatologyLifeQualityIndex(CDLQI)

The CDLQI is a 10-item, validated questionnaire used in clinical practice and clinical trials to assess the impact of AD disease symptoms and treatment on Quality of Life (QoL) in children. The format is a simple response to 10 items, which assess QoL over the past week. For each item, the scale is rated as follows:

- 0 = Not at all = Not relevant
- 1 = Only a little
- 2 = Quite a lot
- 3 = Very much = yes = prevent school

In question 7, with an overall scoring system of 0 to 30; a high score is indicative of a poor QOL. For general inflammatory skin conditions a change in CDLQI score of at least 4 points is considered clinically important. The CDLQI will be assessed at the scheduled and unscheduled clinic visits according to [Appendix 10.2](#).

Handling missing items from CDLQI:

- a. If one question is left unanswered this is scored 0 and the scores are summed and expressed as usual out of a maximum of 30.
- b. If two or more questions are left unanswered the questionnaire is not scored.
- c. If two or more response options are ticked for one question, the response option with the highest score should be recorded.
- d. The CDLQI can be analyzed by calculating the score for each of its six sub-scales. When using sub-scales, if the answer to one question in a sub-scale is missing, that sub-scale should not be scored:

Symptoms and feelings	Questions 1,2	Score maximum 6
Leisure	Questions 4, 5 and 6	Score maximum 9
School or holidays	Question 7	Score maximum 3
Personal relationships	Questions 3 and 8	Score maximum 6
Sleep	Question 9	Score maximum 3
Treatment	Question 10	Score maximum 3

### PatientOrientedEczemaMeasure(POEM)

The POEM is a 7-item, validated questionnaire used in clinical practice and clinical trials to assess disease symptoms in children and adults with atopic eczema ([Charman 2004](#)). The format is patient response to 7 items (dryness, itching, flaking, cracking, sleep loss, bleeding, and weeping) based on symptom frequency during the past week (i.e., 0 = 'no days', 1 = '1 to 2 days', 2 = '3 to 4 days', 3 = '5 to 6' days, and 4 = 'every day'). The total score is the sum of the 7 items which is ranged from 0 to 28; a high score is indicative of a poor QOL. The following POEM banding scores have been established ([Charman 2004](#)):

- 0 to 2 = Clear or almost clear
- 3 to 7 = Mild eczema
- 8 to 16 = Moderate eczema
- 17 to 24 = Severe eczema
- 25 to 28 = Very severe eczema

If two or more response options are selected for a question, then the response option with the highest score is recorded. If one question of the seven is left unanswered, then that question is scored as 0 and the scores are summed and expressed as usual out of a maximum of 28. If two or more questions are left unanswered, then the questionnaire is not scored and is set to missing.

### HospitalAnxietyandDepressionScale(HADS)

The HADS is a tool widely used to detect states of anxiety and depression in a general hospital setting. The 14 items on the questionnaire, assessing how the patient has been feeling in the past week, include 7 items that are related to anxiety (odd numbered questions) and 7 items that are related to depression (even numbered questions). Questions 2, 4, 7, 9, 12, and 14 are scored from 0 (less distress) to 3 (greater distress) according to the content of the item. Questions 1, 3, 5, 6, 8, 10, 11, and 13 are reverse scored from 0 (greater distress) to 3 (less distress). A person can score between 0 and 21 for each subscale (anxiety and depression). A high score is indicative of a poor state. Scores of 11 or more on either subscale are considered to be a 'definite case' of psychological morbidity, while scores of 8–10 represents 'probable case' and 0 – 7 'not a case' ([Zigmond 1983](#)).

For each sub-scale: if one question is missing, the response will be imputed as the mean of the remaining six questions. If more than one question is missing, then the subscale is set to missing. The total score is the sum of the two sub-scores.

The questionnaire will be administered only to the subset of patients who fluently speak a language in which the questionnaire is presented (based on availability of validated translations in participating countries), at time points according to [Appendix 10.2](#).

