#### 6.2.2.7. Patient-Assessed Hospital Anxiety and Depression Scale

The HADS is an instrument for screening anxiety and depression in non-psychiatric populations; repeated administration also provides information about changes to a patient's emotional state (Zigmond 1983, Herrmann 1997). The HADS consists of 14 items, 7 each for anxiety and depression symptoms; possible scores range from 0 to 21 for each subscale. The following cut-off scores are recommended for both subscales: 7 to 8 for possible presence, 10 to 11 for probable presence, and 14 to 15 for severe anxiety or depression. The questionnaire will be administered only to the subset of patients who fluently speak a language in which the

questionnaire is presented (based on availability of validated translations in participating countries), at time points according to section 6.1.

The HADS is provided in the study reference manual.

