## 4. ANALYSIS VARIABLES

### 4.1. Demographic and Baseline Characteristics

The following demographic and baseline characteristics variables will be summarized:

- Demographic variables: Age at screening (year), age group ( $\geq 15$  to  $< 18$ ,  $\geq 12$  to  $< 15$ ), sex, ethnicity, race, baseline weight (kg) with grouping ( $< 60$  kg,  $\geq 60$  kg), height (m), BMI ( $\text{kg}/\text{m}^2$ ) with grouping ( $< 20$ ,  $\geq 20$ )
- Baseline characteristics: Duration of AD disease with grouping ( $< 13$  years,  $\geq 13$  years), Peak Pruritus numerical rating scale (NRS), Pruritus Categorical Scale (PCS), Investigator's Global Assessment (IGA) score, Eczema Area and Severity Index (EASI) score, SCORing Atopic Dermatitis (SCORAD) score, Body Surface Area (BSA) affected by Atopic Dermatitis, Patient global assessment of disease status, Patient Oriented Eczema Measure (POEM), Children's Dermatology Life Quality Index (CDLQI), Global Individual Signs score (GISS), Hospital Anxiety and Depression Scale (HADS) total score, HADS-Anxiety subscale score, HADS-Depression subscale score, Asthma Control Questionnaire (ACQ-5), and Total Nasal Symptom Score (TNSS), Patients with inadequate response to topicals (Yes/No) with the reasons for patients who are "No" for inadequate response to topicals

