#### Analysis of incidence of TEAE-related variables

- Incidence of skin infection TEAE (excluding herpetic infections) from baseline through week 16
- Incidence of treatment-emergent serious adverse events from baseline through week 16

These endpoints will be analyzed for patient in SAF. The week 16 treatment period is defined in Section 3.2. The Cochran-Mantel-Haenszel test adjusted for randomization strata will be used for the percentage of patients with events described above through week 16.

Multiplicity Considerations

The following multiplicity adjustment approach, a hierarchical procedure, will be used to control the overall Type-I error rate at 0.05 for the primary endpoint and the secondary endpoints across the 2 dupilumab dose regimens versus placebo. Each hypothesis will be formally tested only if the preceding one is significant at the 2-sided 0.05 significance level. The hierarchical testing order is shown in below table (all comparisons are with the placebo).

	Endpoints	Dupilumab	
		Q4W group	Q2W group
Primary endpoint	Proportion of patients with IGA 0 to 1 (on a 5-point scale) at week 16	10	1
Co-primary endpoint for ex-US countries, key secondary for US	Proportion of patients with EASI-75 ( $\geq 75\%$ improvement from baseline) at week 16	9	2
Key Secondary endpoints	Percent change in EASI score from baseline to week 16	11	3
	Percent change from baseline to week 16 in weekly average of daily peak Pruritus NRS	12	4
	Proportion of patients with improvement (reduction) of weekly average of daily peak Pruritus NRS $\geq 3$ from baseline to week 16	13	5
	Proportion of patients with improvement (reduction) of weekly average of daily peak Pruritus NRS $\geq 4$ from baseline to week 16	14	6
Secondary endpoints	Proportion of patients with EASI-50 at week 16	15	7
	Proportion of patients with EASI-90 at week 16	16	8
	Time to onset of effect on pruritus during the 16-week treatment period ( $\geq 3$ point reduction of weekly average of peak Pruritus NRS from baseline)	25	17
	Time to onset of effect on pruritus during the 16-week treatment period ( $\geq 4$ point reduction of weekly average of peak Pruritus NRS from baseline)	26	18
	Change from baseline to week 16 in percent BSA affected by AD	27	19
	Percent change from baseline to week 16 in SCORAD	28	20
	Change from baseline to week 16 in CDLQI	29	21
	Change from baseline to week 16 in POEM	30	22

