	Change from baseline to week 16 in weekly average of daily peak Pruritus NRS	31	23
	Percent change from baseline to week 4 in weekly average of daily peak Pruritus	32	24
	Change from baseline to week 16 in HADS	35	33
	Proportion of patients with improvement (reduction) of weekly average of daily peak Pruritus NRS $\geq 4$ from baseline to week 4	36	34
	Incidence of skin-infection TEAEs (excluding herpetic infections) through week 16	39	37
	Incidence of serious TEAEs through week 16	40	38

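### The SAP's HADS scoring rule codes eight of 14 items in the opposite direction to the stated scale, and no step re-aligns them before items are imputed and summed

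*SAP*

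**What the plan says.** The HADS paragraph of SAP 4.4.2 assigns the odd-numbered items to anxiety and the even-numbered items to depression. Items 2, 4, 7, 9, 12 and 14 run from 0 for less distress to 3 for greater distress. For the other eight it says: "Questions 1, 3, 5, 6, 8, 10, 11, and 13 are reverse scored from 0 (greater distress) to 3 (less distress").

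The paragraph then gives each subscale a range of 0 to 21 and states: "A high score is indicative of a poor state". A subscale score of 11 or more is a definite case, 8 to 10 a probable case and 0 to 7 not a case. For a missing item within a subscale, "if one question is missing, the response will be imputed as the mean of the remaining six questions". Finally, "The total score is the sum of the two sub-scores".

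Protocol 6.2.2.7 gives no item-level coding, but its cut-offs also rise with severity: "10 to 11 for probable presence, and 14 to 15 for severe anxiety or depression".

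HADS scores are used in three places:

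- SAP 4.1 lists a total score and also "HADS-Anxiety subscale score, HADS-Depression subscale score" among the baseline characteristics.
- SAP Appendix 10.1 lists change and percent change from baseline.
- The hierarchy table in SAP 5.7.2 places "Change from baseline to week 16 in HADS" at rank 33 for Q2W and rank 35 for Q4W.

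**The concern.** The anchors given for eight of the 14 items contradict the stated direction of the scale. If items pointing in opposite directions are added, improvement on one group cancels improvement on the other. The sum then no longer measures distress, and the case cut-offs have no meaning. The mean-of-six rule fails for the same reason, because it fills a gap in one direction with values coded in the other.

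HADS is part of the type I error-controlled chain, where "Each hypothesis will be formally tested only if the preceding one is significant at the 2-sided 0.05 significance level". A mis-scored HADS at rank 33 could therefore also decide whether ranks 34 to 40 are tested.

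A smaller, separate point is that the tested endpoint says only HADS, although the SAP defines a total and two subscales.

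**Working it through.** **Inputs (all from SAP 4.4.2).** The two item lists cover all 14 items once, with no overlap.

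| Score | Forward items (3 = greater distress) | Opposite items (3 = less distress) |
|---|---|---|
| Anxiety (odd) | 7, 9 (2 items) | 1, 3, 5, 11, 13 (5 items) |
| Depression (even) | 2, 4, 12, 14 (4 items) | 6, 8, 10 (3 items) |
| Total | 6 items | 8 items |

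**The plan's own range.** Seven items × 3 = 21 per subscale. This reproduces under either coding, so the range does not reveal the problem. Item-level summation is not written out, but the range and the rule for the total imply it.

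**Direction.** Let every item sit at distress level d (0 to 3). The literal score is forward × d + opposite × (3 − d). The aligned score is (forward + opposite) × d.

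| Score | No distress: literal | No distress: aligned | Maximum distress: literal | Maximum distress: aligned |
|---|---|---|---|---|
| Anxiety | 5 × 3 = 15 | 0 | 2 × 3 = 6 | 21 |
| Depression | 3 × 3 = 9 | 0 | 4 × 3 = 12 | 21 |
| Total | 24 | 0 | 18 | 42 |

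Read literally, a patient without distress is a definite case of anxiety under the SAP and falls at the Protocol's severe cut-off of 14 to 15. A maximally distressed patient has an anxiety score of 6, which is not a case.

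**Change.** For a one-point improvement on every item, the literal change is opposite − forward:

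- anxiety: 5 − 2 = +3, against −7 when aligned
- depression: 3 − 4 = −1, against −7
- total: 8 − 6 = +2, against −14

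**When the sign is still right.** Forward items must improve more than opposite/forward times as much as the opposite items: 8/6 = 1.33 for the total, 5/2 = 2.5 for anxiety and 3/4 = 0.75 for depression. Depression therefore keeps the right sign under equal item effects, but most of the effect is lost.

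**Imputation.** Suppose item 7 is missing. With no distress, the mean of the other six anxiety items is (5 × 3 + 0)/6 = 2.5 instead of 0. With maximum distress it is (5 × 0 + 3)/6 = 0.5 instead of 3.

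**What could happen at rank 33 (illustration on assumed inputs).** The documents give no HADS effect size, SD or inter-item correlation. Assume 80 per arm, the same benefit of d SD on every item (here d is an effect size) and a common correlation ρ between aligned items. The literal total then has a mean shift of (8 − 6)d = 2d in the wrong direction. Its variance is 14(1 − ρ) + (8 − 6)²ρ = 14 − 10ρ, so the standardized effect is 2d/√(14 − 10ρ). Using a two-sided t-test at 0.05 with 158 df (noncentral t):

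| d | ρ | Standardized effect | Significant, wrong direction | Significant, benefit | Not significant |
|---|---|---|---|---|---|
| 0.20 | 0.2 | 0.115 | 10.9% | 0.36% | 89% |
| 0.50 | 0.6 | 0.354 | 60.4% | below 0.01% | 40% |

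These rows are the two ends of the range examined (d 0.20 to 0.50, ρ 0.2 to 0.6).

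**The case against.** The strongest defence is that reverse scoring normally names the re-alignment itself, and that the bracketed anchors only describe the order in which the response options are printed. On that reading, the high-is-poor statement, the cut-offs, the imputation rule and the Protocol's severity bands all tell a competent programmer to use aligned coding. The Protocol says the instrument is provided in the study reference manual, which is not available here, so whether any score would really be wrong cannot be known from these documents.

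That limits the consequence but does not rescue the text. The anchors attach 0 to greater distress. If they describe the result of the reversal, the result is wrong; if they describe raw values, the reversal is missing, and so is its order relative to imputation. SAP 1 presents the plan as a comprehensive and detailed description of the analysis, and the HADS paragraph does not point to the manual for scoring.

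Other parts of the objection stand:

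- Rank 33 is tested only if ranks 1 to 32 all succeed. The plan's own power for rank 10 (Q4W, IGA 0 or 1) is 88%, so under its assumptions rank 33 is reached at most 88% of the time.
- Ranks 34 to 40 are low-priority: itch response at week 4, Q4W HADS, and two adverse event incidences per regimen.
- The rank 33 illustration rests on assumed inputs and a plain t-test, not the planned multiple imputation with ANCOVA. It takes 80 per arm, although HADS is given only to patients fluent in an available language.
- Reading an unqualified HADS as the total is reasonable, so naming the score is a clarification.

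**Conclusion.** The scoring rule is wrong as written. The contradiction follows from the SAP's own item lists and needs no outside source or statistical assumption. Followed literally, it reverses the direction of the anxiety and total scores when all items move together, reduces depression to one seventh of its true change (−1 against −7), and distorts imputed items. The baseline HADS summaries, the HADS change analyses and the tests at ranks 33 and 35 would then be invalid.

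The downstream effect is conditional on literal programming and on reaching rank 33. A non-significant result there would leave ranks 34 to 40 untested. That is not certain, because the gate is two-sided with no stated direction and could be passed on an apparent worsening. Ranks 1 to 32 are untouched. It should be corrected before database lock.

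**What to change.** Replace the scoring sentence in SAP 4.4.2 with a rule to this effect: all 14 items enter the subscale sums coded 0 = least to 3 = greatest distress; where the raw coding of items 1, 3, 5, 6, 8, 10, 11 and 13 runs the other way, each is first replaced by 3 minus its raw value; a missing item is imputed only after this alignment.

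In SAP 5.7.2, state whether the total or a named subscale is tested at ranks 33 and 35.

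Then check the derivation program and the raw response coding against the instrument in the study reference manual. A simple test is that a record with no distress on any item must give 0, 0 and 0, and one with maximum distress 21, 21 and 42.

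The cost is one or two SAP sentences and a program check before database lock. No data collection, sample size or testing order changes.
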